6.5.1.1 Dose adjustments for ruxolitinib hematologic safety

Dose reductions or interruptions for worsening cytopenias attributed to ruxolitinib are permitted in order to allow the subject to continue on the study treatment. Doses adjustments for different ranges of cytopenias are described in [Table 6-3](#). The objective of the dose adjustment rules is to optimize treatment response for each individual subject while avoiding significant cytopenias. Dose adjustment steps for ruxolitinib are listed in [Table 6-4](#) and [Table 6-5](#).

For any subject who develops severe worsening cytopenias necessitating abrupt interruption of ruxolitinib, flare of cGvHD is expected to occur. To avoid significant cGvHD flare during abrupt ruxolitinib interruption, the subject's corticosteroid dose should be maintained or increased to ≥ 0.4 mg/kg/day methylprednisolone (or equivalent prednisone to ≥ 0.5 mg/kg/day) for a minimum 7 days after abrupt cessation of ruxolitinib.

Ruxolitinib dosing may be restarted or increased following recovery of the hematologic parameter(s) to acceptable levels. The objective for restarting or escalating after a reduction for hematologic safety is to find the highest safe dosing regimen of ruxolitinib for each subject that is necessary to obtain a clinical response, with increases in dose not more than in increments of 5 mg BID and not more often than every 2 weeks. See [Table 6-5](#).

Treatment with ruxolitinib may be delayed up to 21 days to allow for resolution of toxicity. Subjects may resume treatment if no medical condition or other circumstance exists that, in the opinion of the Investigator, would make the subject unsuitable for further participation in the study. The Investigator should contact the Novartis medical monitor to discuss cases where treatment has been delayed for more than 14 days before restarting treatment.

Transfusions are allowed during study treatment, if needed.

6.5.1.2 Dose adjustments for ruxolitinib non-hematologic safety

Dose reductions or interruptions for non-hematologic toxicity attributed to ruxolitinib are permitted in order to allow the subject to continue on ruxolitinib. Dose adjustments for different ranges of non-hematologic toxicity are described in [Table 6-3](#). The objective of the dose adjustment rules is to optimize treatment response for each individual subject while avoiding significant non-hematologic toxicities.

As organ toxicities are relatively common in alloSCT subjects, any adverse event must be assessed to determine whether it is suspected to be related to ruxolitinib treatment. Ruxolitinib dose adjustments are only required for adverse events that are suspected to be related to the study drug. This has particular relevance in evaluation of elevated serum creatinine, as

elevations related to CNI administration are often seen. Dose adjustment of CNI will follow institutional guidelines and investigator judgement, with CNI dose reductions anticipated if rising creatinine occurs, to potentially alleviate the need for ruxolitinib dose reductions.

Treatment with ruxolitinib may be delayed up to 21 days to allow for resolution of toxicity. Subjects may resume treatment if no medical condition or other circumstance exists that, in the opinion of the Investigator, would make the subject unsuitable for further participation in the study.

Ruxolitinib must be permanently discontinued upon any one of the following non-hematological adverse events attributed to study drug that fails to resolve to Grade 2 or better within 14 days or if a lower re-start dose or administration schedule subsequent to any of the following non-hematologic toxicities is either not available or likely to be clinically ineffective:

- occurrence of a Grade 4 laboratory or non-laboratory abnormality attributable to ruxolitinib
- occurrence of a Grade 3 laboratory or non-laboratory abnormality attributable to ruxolitinib that remains at Grade 3 or worse for greater than 14 days

If any one or more of the treatment discontinuation criteria are met prior to Cycle 7 Day 1, the subject will be considered to be a non-responder in terms of the primary endpoint.

Subjects who permanently discontinue ruxolitinib for reasons other than achieving a CR or PR prior to completion of 39 cycles on study, will complete the safety follow-up visit and enter the early discontinuation follow-up (as described in [Table 8-1](#)) and may be treated per Institutional practice.

The date the subject discontinued ruxolitinib and the specific reason for permanent study treatment discontinuation will be recorded in the eCRF.

Table 6-3 Criteria for dose reduction / interruption and re-initiation of ruxolitinib treatment for adverse drug reactions

Dose modifications for ruxolitinib for adverse events^a suspected to be drug-related	
Worst toxicity	
Investigations (Hematologic)	
Neutropenia (ANC)	
Grade 1 (ANC < LLN - 1500/mm ³)	Recommendation: Maintain dose level.
Grade 2 (ANC < 1500 - 1000/mm ³)	Recommendation: Maintain dose level.
Grade 3 (ANC < 1000 - 750/mm ³)	Recommendation: Maintain dose level.
Grade 3 (ANC < 750 - 500/mm ³)	Mandatory: Reduce 1 dose level (see Table 6-4), monitor ANC daily until resolved to ≤ Grade 2, then resume initial dose level.
Grade 4 (ANC < 500/mm ³)	Mandatory: Hold dose, monitor ANC daily until resolved to ≤ Grade 3, then resume at reduced 1 dose level. If resolves to ≤ Grade 2, can resume initial dose level. Ruxolitinib must be permanently discontinued if fails to resolve to Grade 2 or better within 14 days. If not resolved in ≤ 21 days the subject must be discontinued.
Febrile neutropenia (ANC < 750/mm ³ , fever ≥ 38.5°C)	Mandatory: Hold dose until resolved, then restart at reduced 1 dose level
Thrombocytopenia	
Grade 1 (PLT < LLN-75,000/mm ³)	Recommendation: Maintain dose level.

Dose modifications for ruxolitinib for adverse events^a suspected to be drug-related	
Worst toxicity	
Grade 2 (PLT < 75,000 - 50,000/mm ³)	Recommendation: Maintain dose level.
Grade 3 (PLT < 50,000 - 25,000/mm ³)	Recommendation: Maintain dose level.
Grade 4 (PLT < 25,000 - 20,000/mm ³)	Recommendation: Maintain dose level.
Grade 4 (PLT < 20,000 - 15,000/mm ³)	Mandatory: Reduce 1 dose level until resolved to ≥20,000/mm ³ . If resolved in ≤ 7 days, then resume initial dose level. If resolved in > 7 days, then maintain at reduced 1 dose level.
Grade 4 (PLT < 15,000/mm ³)	Mandatory: Hold dose until resolved to ≥20,000/mm ³ , then resume at reduced 1 dose level. If resolves to ≤ Grade 3, can resume initial dose level. If not resolved in ≤14 days, the subject must be discontinued.
Investigations (Renal)	
Serum creatinine	
Grade 1 (> ULN - 1.5 x ULN)	Recommendation: Maintain dose level.
Grade 2 (> 1.5 - 3.0 x ULN)	Mandatory: Reduce 1 dose level until resolved to ≤ Grade 1 or baseline, then resume initial dose level.
Grade 3 (> 3.0 - 6.0 x ULN)	Mandatory: Hold dose until resolved to ≤ Grade 2, then restart at reduced 1 dose level. If resolves to ≤ Grade 1, can resume initial dose level.
Grade 4 (> 6.0 x ULN)	Mandatory: Discontinue subject from study treatment.
Investigations (Hepatic)	
Total Bilirubin elevation	
> ULN - 1.5 x ULN	Recommendation: Maintain dose level.
> 1.5 - 3.0 x ULN	Recommendation: Maintain dose level.
> 3.0 - 10.0 x ULN*	Mandatory: Interrupt treatment. Monitor LFTs ^b weekly or more frequently if clinically indicated, until resolved to ≤ 3.0 x ULN: If resolved in ≤ 14 days, then resume same dose level. If resolved in > 14 days, then resume at reduced one dose level.
> 10.0 x ULN*	Mandatory: Interrupt treatment. Monitor LFTs ^b weekly, or more frequently if clinically indicated, until resolved to ≤ 3.0 x ULN: If resolved in ≤ 14 days, then resume at reduced 1 dose level. If resolved in > 14 days, then discontinue subject from study treatment. The subject should be monitored weekly (including LFTs ^b), or more frequently if clinically indicated, until total bilirubin has resolved to baseline or stabilization over 4 weeks.
AST or ALT elevation	
> ULN - 3.0 x ULN	Recommendation: Maintain treatment and dose level.
If normal at baseline: > 5.0 x ULN for more than 2 weeks, OR > 10 x ULN If elevated at baseline: >3 x baseline and > 10 x ULN	Mandatory: Interrupt treatment. Repeat LFTs ^b as soon as possible, preferably within 48-72 hours from awareness of the abnormal results; Monitor LFTs ^b weekly, or more frequently if clinically indicated, until resolved to ULN or to baseline. : If resolved, then resume at reduced one dose level.

Dose modifications for ruxolitinib for adverse events^a suspected to be drug-related	
Worst toxicity	
> 20.0 x ULN:	Mandatory: Permanently discontinue patient from study treatment.. Repeat LFTs ^b as soon as possible, preferably within 48-72 hours from awareness of the abnormal results; monitor LFTs ^b weekly, or more frequently if clinically indicated, until resolved to baseline or stabilization over 4 weeks.
Combined ^celevations of AST or ALT and total bilirubin	
For participants with normal baseline ALT and AST and total bilirubin value: AST or ALT > 3.0 x ULN combined with total bilirubin > 2.0 x ULN without evidence of cholestasis ^d OR For participants with elevated baseline AST or ALT or total bilirubin value: [AST or ALT > 3 x baseline OR [> 8.0 x ULN], whichever is lower combined with Total bilirubin > 2 x baseline AND >2.0 x ULN Note: For participants with Gilbert's syndrome, at least 2-fold increase in direct bilirubin	Mandatory: Interrupt treatment and adjudicate for DILI: Repeat as soon as possible, preferably within 48 hours from awareness of the abnormal results, then with weekly monitoring of LFTs ^b , or as clinically indicated, until AST, ALT, or total bilirubin have resolved \leq ULN or to baseline. Refer to Section 6.5.2.1 (for additional follow-up evaluations as applicable.) If causality assessment indicates that DILI is probable: Permanently discontinue participant from treatment. If not DILI: Treat the identified cause according to institutional guidelines. Once resolved, resume at reduced one dose level.
Investigation (metabolic)	
Asymptomatic amylase and/or lipase elevation**	
Grade 1 (> ULN - 1.5 x ULN)	Recommendation: Maintain dose level.
Grade 2 (> 1.5 - 2.0 x ULN)	Recommendation: Maintain dose level.
Grade 3 (> 2.0 - 5.0 x ULN)	Recommendation: Hold dose of until resolved to Grade \leq 2, then: If resolved in \leq 7 days, then resume same dose level. If resolved in > 7 days, then resume at reduced 1 dose level.
Grade 4 (> 5.0 x ULN)	Recommendation: Discontinue subject from study treatment.
Vascular disorders	
Hypertension	
CTCAE Grade 3	Recommendation: Reduce 1 dose level until resolved to \leq Grade 2, then increase by one dose level.
CTCAE Grade 4	Mandatory: Discontinue subject from study treatment.
Gastro intestinal	
Pancreatitis	
Grade 2	Recommendation: Maintain dose level.
Grade \geq 3	Mandatory: Discontinue subject from study treatment.
Diarrhea***	
Grade 1	Recommendation: Maintain dose level. May initiate anti-diarrhea treatment.
Grade 2	Recommendation: Maintain dose level. May initiate anti-diarrhea treatment.
Grade 3	Recommendation: Reduce 1 dose level until resolved to \leq Grade 2, then increase by one dose level.
Grade 4	Mandatory: Discontinue subject from study treatment.
Skin and subcutaneous tissue disorders	
Rash/photosensitivity	

Dose modifications for ruxolitinib for adverse events^a suspected to be drug-related	
Worst toxicity	
Grade 1	Recommendation: Maintain dose level.
Grade 2	Recommendation: Maintain dose level.
Grade 3	Recommendation: Reduce 1 dose level until resolved to ≤ Grade 2, then: If resolved in ≤ 7 days, increase by one dose level. If resolved in > 7 days, then maintain the reduced dose level.
Grade 4	Mandatory: Discontinue subject from study treatment.
Other adverse events	
Grade 1 or 2	Recommendation: Maintain dose level.
Grade 3	Recommendation: Hold dose until ≤ grade 2, then decrease 1 dose level
Grade 4	Recommendation: Discontinue subject from study treatment.
All dose modifications should be based on the worst preceding toxicity.	
For dose level refer to Table 6-3 and Table 6-4	
^a Common Terminology Criteria for Adverse Events (CTCAE Version 4.03)	
^b Core LFTs consist of ALT, AST, GGT, total bilirubin (fractionated (direct and indirect), if total bilirubin > 2.0 x ULN), and alkaline phosphatase (AP) (fractionated (quantification of isoforms), if alkaline phosphatase > 2.0 x ULN.)	
^c "Combined" defined as total bilirubin increase to the defined threshold concurrently with ALT/AST increase to the defined threshold.	
If combined elevations of AST or ALT and total bilirubin do not meet the defined thresholds, please follow the instructions for isolated elevation of total bilirubin and isolated elevation of AST/ALT, and take a conservative action based on the degree of the elevations (e.g. discontinue treatment at the situation when omit dose is needed for one parameter and discontinue treatment is required for another parameter). After all elevations resolve to the defined thresholds that allow treatment re-initiation, re-start the treatment either at the same dose or at one dose lower if meeting a criterion for dose reduction.	
^d "Cholestasis" defined as ALP elevation (> 2.0 x ULN and R value < 2) in patients without bone metastasis or elevation of ALP liver fraction in patients with bone metastasis	
Note: The R value is calculated by dividing the ALT by the ALP, using multiples of the ULN for both values. It denotes whether the relative pattern of ALT and/or ALP elevation is due to cholestatic (R ≤ 2), hepatocellular (R ≥ 5), or mixed (R > 2 and < 5) liver injury	
* Note: If total bilirubin > 3.0 x ULN is due to the indirect (non-conjugated) component only, and hemolysis as the etiology has been ruled out as per institutional guidelines (e.g., review of peripheral blood smear and haptoglobin determination), then reduce 1 dose level and continue treatment at the discretion of the Investigator.	
** Note: A CT scan or other imaging study to assess the pancreas, liver, and gallbladder must be performed within 1 week of the first occurrence of any ≥ Grade 3 of amylase and/or lipase. If asymptomatic Grade 2 elevations of lipase and/or amylase occur again at the reduced dose, subjects will be discontinued permanently from study treatment.	
*** Note: antidiarrheal medication is recommended at the first sign of abdominal cramping, loose stools or overt diarrhea	

Table 6-4 Dose reduction steps for ruxolitinib

Dose Reduction steps of ruxolitinib *			
Groups	Starting dose level – 0	Dose level – 1	Dose level – 2
Group 1	10 mg BID	5 mg BID	5 mg QD**
Group 2	5mg BID	5 mg QD or 2.5mg BID	Not applicable

Dose Reduction steps of ruxolitinib *			
Group 3	4 mg/m ² BID	50% of starting dose BID	Not applicable
Group 4	Starting dose BID***	50% of starting dose BID	Not applicable
*Dose reduction should be based on the worst toxicity demonstrated at the last dose.			
**Dose reduction below 5 mg total daily dose is not allowed.			
***Based on prior data collected from [CINC424F12201] and [CINC424C2301], [CINC424D2301].			

Subjects who have had a dose reduction of ruxolitinib in order to manage toxicity may resume treatment at the previous dose if hematologic/non-hematologic parameters meet the required threshold(s).

Table 6-5 Dose re-escalation levels for ruxolitinib

Dose Re-escalation*			
	Current dose	First dose escalation	Second dose escalation
Group 1	5 mg QD	5 mg BID	10 mg BID
	5 mg BID	10 mg BID	*
Group 2	5mg QD or 2.5 mg BID	5mg BID	Not applicable
Group 3	50% of starting dose BID	Starting dose BID	Not applicable
Group 4	50% of starting dose BID	Starting dose BID	Not applicable

Except for Group 1, all other dose escalations are examples and may not reflect the actual starting dose.
*Dose increases may not exceed 10 mg BID, in increments of 5 mg and not more often than every 2 weeks.

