12.4.3 Handling of missing values/censoring/discontinuations

Subjects with missing assessments that prevent the evaluation of the primary endpoint will be considered as non-responders. This includes missing cGvHD assessments at baseline and Cycle 7 Day 1.

Subjects who discontinue study treatment should return for the regular assessments indicated in [Section 9.1](#). Addition or initiation of a new systemic therapy before Cycle 7 Day 1 will be considered a treatment failure, and subjects will be counted as non-responder in the primary analysis.

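### Protocol 6.5.1.2 makes subjects who meet its discontinuation criteria before Cycle 7 Day 1 non-responders, but Protocol 12.4.3 and SAP 2.5.3 leave the rule out

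*Protocol*

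**What the plan says.** Protocol 6.5.1.2 requires permanent discontinuation for certain ruxolitinib-attributed non-hematologic events that do not resolve in time or leave no workable lower dose. Two are listed: a Grade 4 abnormality, and "occurrence of a Grade 3 laboratory or non-laboratory abnormality attributable to ruxolitinib that remains at Grade 3 or worse for greater than 14 days". It then states that where such "criteria are met prior to Cycle 7 Day 1, the subject will be considered to be a non-responder in terms of the primary endpoint". No exception is given.

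Protocol 12.4.3, the section on missing data and discontinuation for the primary endpoint, gives two routes to non-response. The first is: "Subjects with missing assessments that prevent the evaluation of the primary endpoint will be considered as non-responders". The second is new systemic therapy before Cycle 7 Day 1 (C7D1). For subjects who stop treatment it says only that they should come back for assessments. SAP 2.5.3 repeats this almost unchanged.

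The 6.5.1.2 rule is also absent from the endpoint definitions (Protocol 12.4.1, SAP 2.5.1) and from SAP 5.4.3. SAP 2.5.1 takes response from the CRF. SAP Section 4 lists one change from the protocol, an added exploratory endpoint.

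**The concern.** Two parts of the protocol give different answers for the same subject, and the SAP carries forward the one without the rule. Followed as written, the SAP can count as a responder someone whom 6.5.1.2 calls a non-responder. The error runs one way, since applying the rule can only remove responders. The report would not show it, because neither the missing-data text nor the list of changes tells the reader that the rule exists.

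**Working it through.** **The plan's own figure.** Protocol 12.8.1 gives probability 0.836 that the lower 90% Clopper-Pearson limit is at least 50% with 42 subjects and a true ORR of 70%. The minimum is 27 responders (limits 0.505 and 0.765), and P(X ≥ 27 | 42, 0.70) = 0.8360. With 46 subjects the minimum is 30, and the probability is 0.8090 against 0.809 in the table. Both reproduce. The point disputes no design figure.

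**Who escapes the two written routes.** Follow-up after early discontinuation (Protocol 9.1.1) lists no cGvHD assessment, so a subject who stops well before C7D1 is normally a non-responder through missing data. To be counted as a responder, the subject needs a CR or PR in the C7D1 window, Study Days 159 to 179 (SAP Table 2-1). There are two ways.

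- (a) The subject stopped shortly before C7D1 and has an end-of-treatment (EOT) or unscheduled assessment in the window. SAP 2.1.1 maps EOT assessments to visit windows. That cGvHD is assessed at EOT is inferred from this, because the relevant row of Table 8-1 is not in the text available.
- (b) The subject met a criterion but was kept on drug or put back on it. Section 6.5.1.2 also says "Treatment with ruxolitinib may be delayed up to 21 days to allow for resolution of toxicity". For Grade 3 creatinine, Table 6-3 says "Mandatory: Hold dose until resolved to ≤ Grade 2, then restart at reduced 1 dose level", with no 14-day limit. Grade 3 rash is managed at a reduced dose: "If resolved in > 7 days, then maintain the reduced dose level". The Grade 3 rows for amylase/lipase, hypertension, diarrhea and other adverse events also set no 14-day limit. For bilirubin above 3 and up to 10 × ULN the table says "If resolved in > 14 days, then resume at reduced one dose level". That row carries no CTCAE grade, so treating it as Grade 3 is an assumption.

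**Size per subject.** Enrollment was 46 (Protocol, Amendment 2). The Full Analysis Set may be slightly smaller.

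- 1/46 = 2.17 points; 1/45 = 2.22 points.
- At about the planned 70%: 32/46 = 69.6% (90% CI 0.566 to 0.806). With one subject moved: 31/46 = 67.4% (0.543 to 0.787).

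**How many subjects.** The documents give none of the shares below; all are assumed.

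Route (a): take the last dose as evenly spread over days 1 to 168 and EOT 0 to 7 days later, each delay equally likely. Last doses on days 159 to 168 always put EOT in the window (10 days). Last doses on days 152 to 158 do so with probability 1/8 to 7/8 (sum 28/8 = 3.5 days). The fraction is 13.5/168 = 0.0804. Expected count = 46 × share stopping before C7D1 × share of those stopping on a 6.5.1.2 criterion × share still in CR/PR × 0.0804.

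Route (b): expected count = 46 × share meeting a criterion and staying on drug × share in CR/PR.

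| Route | Low | Central | High |
|---|---|---|---|
| (a) shares | 10%, 10%, 20% | 25%, 25%, 40% | 40%, 50%, 60% |
| (a) expected subjects | 0.01 | 0.09 | 0.44 |
| (b) shares | none | 1%, 60% | 3%, 70% |
| (b) expected subjects | 0 | 0.28 | 0.97 |

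The central total is 0.09 + 0.28 = 0.37 subjects. For route (b), the chance of at least one affected subject is 1 − (1 − 0.006)^46 = 24% in the central case and 1 − (1 − 0.021)^46 = 62% in the high case. At a 70% response rate, route (b) yields one expected responder only if 1/(46 × 0.70) = 3.1% of subjects, or 1/0.70 = 1.4 of 46, meet a criterion and stay on drug.

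**The case against.** The strongest reply has four parts.

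- **The SAP follows the protocol's statistics section.** This stands. A reader might infer that the SAP quietly dropped a protocol rule. The documents do not support that: SAP 2.5.3 matches Protocol 12.4.3, and the conflict begins between Protocol 6.5.1.2 and 12.4.3. It remains unresolved all the same.
- **Table 6-3 does not override 6.5.1.2.** This largely stands. A reader might infer that the protocol plainly lets sites keep a subject on drug through more than 14 days of attributable Grade 3 toxicity. But 6.5.1.2 makes permanent discontinuation mandatory, and the 21-day hold can be read as time for recovery beyond Grade 2. The most that can be said is that some rows appear to allow continuation. Route (b) therefore needs a site to follow the row rather than the section text.
- **The counts are guesses, and zero is the likeliest result.** This stands. The timing model for route (a) is also rough: after a hold, the last dose can precede the 14-day criterion by about two weeks.
- **The 14-day criterion cannot always be derived.** This stands for laboratory values. They become adverse events only if symptomatic, clinically significant or needing therapy (Protocol 10.1.1). Programmed grades use the values alone and carry no causality (SAP 2.8.3). Scheduled visits are four-weekly from Cycle 2 to Cycle 7.

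Sites or programming specifications may apply the rule outside these documents. That is unknown; no step in the protocol or SAP does so. The sensitivity analysis in SAP 2.5.4 is no substitute: it excludes protocol deviators, such as those with holds over 21 days who stayed on drug, and does not count subjects who met a 14-day criterion as non-responders.

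**Conclusion.** The contradiction is real and the confidence in it is high. Its effect is minor: ORR is overstated by 2.2 points per affected subject, probably 0 to 1 subject, with low confidence in the count because every share is assumed.

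A reader might infer that the omission could change the trial's conclusion. At exactly 30 of 46 responders, moving one takes the lower 90% limit from 0.521 to 0.499. That is a boundary case, not a prediction. The 50% figure is a sample-size target (Protocol 12.8.1), and SAP 2.5.2 plans no test, so no decision rule changes.

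A reader might also infer that the rule covers every discontinuation. Read in place, it refers to the non-hematologic criteria listed just above it. Hematologic criteria and holds over 21 days come in only on a wider reading that the text does not settle.

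**What to change.** Either of two changes resolves it.

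1. Add to SAP 2.5.3 and Protocol 12.4.3 that a subject who meets a treatment discontinuation criterion of Protocol 6.5.1.2 before C7D1 is a non-responder, even if a response is recorded in the C7D1 window.
2. Leave the primary result unchanged and declare the departure in SAP Section 4. In the final CSR, report how many responders met a criterion before C7D1, and the ORR with them counted as non-responders.

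The second is easier now. The interim primary result exists, and SAP 2.5 does not repeat that analysis unless data changed, so under the first option a changed count would have to be shown as a correction.

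Either way, state whether hematologic criteria and holds over 21 days are included. Identify subjects from the recorded discontinuation date and reason (Protocol 6.5.1.2) and from adverse event grade, causality and dates. Protocol 10.1.1 has the improvement of Grade 3 and 4 events dated. Limit the derivation to reported adverse events and recorded discontinuations, because other laboratory abnormalities lack causality and may not show 14-day persistence.

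The cost is one sentence or one note, plus one derivation from data already collected. Only current responders need checking, about 0.70 × 46 = 32 at the planned rate.

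### Table 6-3's Grade 4 neutropenia cell sets a Grade 3 restart against a 14-day Grade 2 stop, and the non-responder rule in Protocol 6.5.1.2 is missing from Protocol 12.4.3 and SAP 2.5.3

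*Protocol*

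**What the plan says.** **The dosing cell.** Table 6-3 marks the Grade 4 neutropenia row as mandatory. The dose is held "until resolved to ≤ Grade 3, then resume at reduced 1 dose level", and the initial dose may resume at Grade 2 or better. Two stop sentences follow: "Ruxolitinib must be permanently discontinued if fails to resolve to Grade 2 or better within 14 days" and "If not resolved in ≤ 21 days the subject must be discontinued". The second names no grade for recovery.

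**The surrounding rules.** Section 6.5.1.1, on hematologic safety, says "Treatment with ruxolitinib may be delayed up to 21 days to allow for resolution of toxicity" and asks investigators to discuss with the medical monitor "cases where treatment has been delayed for more than 14 days before restarting treatment". Sections 6.5.1 and 9.1.1 set a general limit: a hold of more than 21 days means permanent discontinuation. Section 6.5.1 makes permanent discontinuation mandatory where Table 6-3 says so, and 9.1.1 lists the 21-day limit in addition to the Table 6-3 stops. Other event-specific 14-day stops exist. For platelets below 15,000/mm³ the rule is "If not resolved in ≤14 days, the subject must be discontinued", and for bilirubin above 10 x ULN it is "If resolved in > 14 days, then discontinue subject from study treatment".

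**The endpoint rule.** Section 6.5.1.2, under its non-hematologic heading, says that a subject who meets any treatment discontinuation criterion before Cycle 7 Day 1 counts as a non-responder for the primary endpoint. Protocol 12.4.3 and SAP 2.5.3 give two routes to non-response: a missing assessment that prevents evaluation, and new systemic therapy before Cycle 7 Day 1. On discontinuation they say only that subjects should return for assessments. SAP Section 4 lists one change from the protocol, an added exploratory endpoint.

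**The concern.** In the cell, the restart threshold is looser than the recovery grade that avoids a permanent stop. A site that follows the restart sentence can have a child back on a reduced dose whom the next sentence removes from treatment for good. The restart after more than 14 days foreseen in 6.5.1.1 has no place once the 14-day stop applies.

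For the endpoint, a programmer working from SAP 2.5.3 has no instruction to apply the 6.5.1.2 rule. A subject whom the protocol calls a non-responder could then be counted as CR or PR in the primary ORR, with nothing in the SAP to show that the two documents differ. Because the rule sits under the non-hematologic heading, it is also unclear whether it reaches a neutropenia or platelet stop.

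**Working it through.** **1. The cell, case by case** (days counted from the start of the hold, which the cell does not specify)

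- Grade 2 by day 10: restart, initial dose allowed, no stop. There is no conflict.
- Grade 3 on day 10 and still Grade 3 on day 15: the restart sentence puts the child back on a reduced dose, and the 14-day sentence then requires a permanent stop. This is a direct conflict.
- Grade 4 until day 16, Grade 2 on day 17: the 14-day sentence stops the child, while 6.5.1.1 foresees a restart after contact with the medical monitor. The two sections conflict.
- Grade 4 beyond day 21: every rule says stop.

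If recovery in the 21-day sentence means Grade 3 or Grade 2, the two grades the cell names, the 14-day sentence always acts first and the 21-day sentence does nothing. It would act only if recovery meant better than Grade 2. It would then stop a child whom the same cell allows back on the initial dose.

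**2. Who could be scored differently on the primary endpoint**

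Most early stoppers become non-responders anyway. The early-discontinuation follow-up listed in Protocol 9.1.1 has no cGvHD response assessment, so the missing-data rule covers them. Two routes remain.

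- *Held more than 21 days but kept on drug.* SAP 2.5.4 has a deviation code for this, WITH01. Such a subject meets the criterion in 6.5.1 and 9.1.1, can still be assessed at Cycle 7 Day 1, and can be CR or PR in the primary analysis. SAP 2.5.4 removes the subject from a sensitivity analysis but does not code a non-response.
- *End-of-treatment (EOT) response inside the Cycle 7 Day 1 window.* SAP Table 2-1 sets the window at Days 159–179 and maps EOT assessments to visits. Table 8-1 places EOT within 7 days of the last dose. For a stop that takes effect at the last dose, EOT on or after Day 159 needs a last dose on or after 159 − 7 = Day 152. A stop before nominal Day 169 needs a last dose by Day 168. That span does not fit a neutropenia non-recovery stop, which is known only about 14 days after the last dose. If EOT then follows within 7 days of the decision (my assumption), the last dose falls between 159 − 21 = Day 138 and 168 − 14 = Day 154. This route also needs a cGvHD assessment at EOT. That row of Table 8-1 is not legible in the text I worked from, although SAP 2.7.1 uses responses up to End of Treatment.

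**3. Size**

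Inputs: n = 46 enrolled (Protocol, Amendment 2), two-sided 90% Clopper-Pearson limits (SAP 2.5.2), assumed true ORR 70% (Protocol 12.8.1). With x responders, the lower limit is the 5% quantile of Beta(x, n − x + 1) and the upper limit is the 95% quantile of Beta(x + 1, n − x).

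The plan's own figures reproduce:
- 27/42 gives 0.505–0.765, and P(X ≥ 27) = 0.836.
- 30/46 gives 0.521–0.768, and P(X ≥ 30) = 0.809.

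One responder recoded moves ORR by 1/46 = 2.17 points:
- From 30/46 to 29/46, the lower limit goes from 0.521 to 0.499.
- From 33/46 to 32/46, the lower limit goes from 0.589 to 0.566.

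**4. Timing**

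Enrollment was complete by 17-Sep-2021. Adding 28 days of screening gives a latest first dose of about 15-Oct-2021. Day 179 is then 11-Apr-2022, and 156 weeks (1,092 days) end on 11-Oct-2024, four days after the SAP date of 07-Oct-2024.

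**The case against.** The strongest reply on the cell is that the documents rank the rules. Sections 6.5.1 and 9.1.1 make Table 6-3 stops binding in addition to the 21-day limit, so the 14-day stop governs and the 21-day sentence is surplus. That stands, and it sets the default fix.

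A reader might go further and infer that the 21-day sentence lets treatment continue to day 21, so that sites face two irreconcilable deadlines. The documents do not support this. The 21-day sentence is itself a stop rule and authorises nothing, and a site that obeys the 14-day stop satisfies both. The 21-day allowance in 6.5.1.1 also still has work elsewhere: the febrile neutropenia row has a hold with no deadline. A reader might also take the 14-day sentence for a stray copy, since 6.5.1.2 applies similar wording only to "non-hematological adverse events attributed to study drug that fails to resolve to Grade 2 or better within 14 days". The 14-day platelet stop in the same table makes that uncertain.

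Two further inferences fail. Flare after abrupt interruption follows the hold, which is mandatory under either deadline, and 6.5.1.1 gives steroid cover for it. The absence of a code for a missed 14-day stop from SAP 2.5.4 shows no gap in deviation capture. That list covers only deviations that may affect the primary endpoint, and SAP 2.3.1 lists all deviations.

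On the endpoint, omission is not contradiction: neither 12.4.3 nor SAP 2.5.3 calls such a subject a responder. WITH01 is itself a deviation that the SAP recognises, and the EOT route is conditional. These points limit the weight. They do not supply the missing instruction.

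**Conclusion.** Both points hold as minor clarifications. In the cell, the conflict is between the Grade 3 restart and the 14-day Grade 2 stop, and between that stop and the later restarts foreseen in 6.5.1.1. The 21-day sentence is redundant.

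For the endpoint, a protocol rule is missing from both analysis sections without being declared dropped, and at least the WITH01 route lets a protocol non-responder be scored as a responder. Each such subject is worth about 2.2 points of ORR, assuming that all 46 enrolled are in the FAS; any exclusion makes it slightly more. The documents do not say how many subjects are affected, and the number may be zero.

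A reader might infer that the primary result is biased or that its conclusion could change. The documents do not support that. The step from 0.521 to 0.499 occurs only at exactly 30/46, the 50% mark is a planning criterion, and no hypothesis is tested. Sample size and power are unchanged, and the cell edit alone does not alter ORR.

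**What to change.** **Cell.** Delete the 21-day sentence from the Grade 4 neutropenia row. State whether a subject already restarted at Grade 3 must stop at day 14, and note the exception in 6.5.1.1. Since treatment is essentially over, the useful step now is for the CSR to state which deadline was applied. The corrected cell also matters if this dose table is reused.

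**Endpoint.** Add the 6.5.1.2 rule to SAP 2.5.3 and Protocol 12.4.3, stating that it covers hematologic stops and holds of more than 21 days. Check whether any subject is affected. If so, report ORR under both codings, saying which is protocol-specified and which the interim CSR used. The rule should not be removed from 6.5.1.2, because that would redefine the primary endpoint after its analysis. Nor should the protocol-specified coding be labelled post hoc.

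**Cost.** One cell edit, a note in 6.5.1.1, one sentence in each analysis section, a check of existing data and, if needed, one extra ORR line. No new data are required. SAP 2.5 does not repeat the primary analysis unless data changed, so the extra line would sit beside the interim result and not replace it.
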